### Preliminary Studies:

[figure not shown]

Figure 2. Significant differences (\* indicates  $p < .010$ ) between healthy controls (HC) and PD groups according to swallowing safety (PA scores; panel A) and disease severity (Hoehn & Yahr scale; panel B).

of various intensities. Our study compared 14 patients with PD to 13 age and sex matched healthy adults (HCs). The results show that people

with PD exhibit blunted magnitude estimation of inspiratory resistive loads as compared with the control group regardless of whether they exhibit measurable decline in swallowing safety, or of disease severity (Figure 2 panels A and B). These data indicate general respiratory sensation is blunted even when dysphagia is not present, and in the early stages of the disease, thus lending preliminary support to the hypothesis that blunted respiratory somatosensation precedes the onset of swallowing deficits in PD.

*Reflex cough sensitivity is blunted in later PD compared to earlier PD and age-matched controls:* In an ongoing study we are measuring sensitivity to the airway irritant capsaicin by examining the perceived UtC. To date, participants include 76 men and women with PD, ranging from 1 to 23 years post-diagnosis and 51 age-matched control participants. Our interim analysis show that participants within 10 years of diagnosis (Figure 3, PD 1-4 and PD 5-9 groups) do not exhibit a significant difference in the UtC sensitivity as compared to the control group, however the PD 10+ group does exhibit a significantly blunted UtC sensitivity compared to controls (Figure 3).

*General respiratory sensation is blunted in PD, independent of disease severity or swallowing safety:* In order to understand whether people with PD experience blunted respiratory somatosensation we conducted a preliminary study to examine the perception and magnitude estimated of inspiratory loads

[figure not shown]

Figure 3. Urge to cough (UtC) sensitivity slope comparison between healthy controls (HC), and PD duration groups. PD1-4 is 1-4 years post PD diagnosis; PD5-9 is 5-9 years post PD diagnosis; PD 10+ is more than 10 years post PD diagnosis. \* is significantly different at  $p < .001$ .

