## **5. Specific Aims:**

The specific aims for this project are:

Aim 1: To determine the relationships between blunted airway somatosensation, reflex cough sensitivity and effectiveness, and swallowing function in people with PD.

Hypothesis 1: We predict that blunted airway somatosensation will appear earlier (years 0 – 5 post-diagnosis) in the disease process than either cough or swallowing dysfunction, and that by 6-10 years post-diagnosis, blunted respiratory somatosensation will correlate with reduced reflexive cough sensitivity and effectiveness, and decline in swallow function and safety.

Specific aim 2: To determine whether measures of discriminative and affective processing of general airway sensation is/are associated with deficits in reflex cough and swallowing function in people with PD.

Hypothesis 2: People with PD will exhibit reduced discriminative processing components of airway stimuli. With disease progression, measures of affective processing components will decline and this will directly correlate with diminished reflex cough sensitivity and swallowing function.

Specific aim 3: To determine whether over-filtering of airway stimuli is associated with swallowing or cough deficits in people with PD.

Hypothesis 3: Over-filtering of airway stimuli will be associated with deficits in reflex cough and swallowing function in people with PD.

Aim 4: Determine the relationships between observable motor aspects of swallowing, cough, and cough sensitivity over a 3-year time period in people with PD.

Hypothesis 4: Swallowing safety and physiology in people with PD will exhibit significant differences over 3 time points, spaced 10 – 18 months apart. For people within 9 years of PD diagnosis, reduced reflex cough sensitivity will not be a sensitive and/or specific indicator of swallowing dysfunction. However, for those with a greater disease duration (10+ years), reflex cough sensitivity will be a sensitive and specific biomarker of swallowing dysfunction.

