#### ***Exclusion criteria:***

1. Neurological disorders other than PD (i.e., stroke, multiple sclerosis, etc.)
2. Difficulty complying due to neuropsychological dysfunction (i.e., severe depression)
3. Allergy to capsaicin or hot peppers
4. History of cancer in the head, neck, or lungs (not including skin cancer on the head/neck that did not require major surgical resection significantly altering anatomy or radiation to head/neck tissue).
5. History of smoking in the past 5 years
6. Any neurological disorder including PD (Healthy control group only)

*Experimental design and procedures:* This prospective experimental study will be completed in one or two study visit(s) taking between 1 and 3 hours each. Testing will be conducted in a quiet clinical research space. Verbal and written informed consent will be obtained by qualified members of the investigative team. Following informed consent, all participants will complete a health history questionnaire to assess inclusion/exclusion criteria (Appendix 1). As well, the consenting investigator will review the electronic medical record to ensure inclusion/exclusion criteria are met.

The experimental protocol will consist of 1.) Review of electronic medical record to determine participant disease status 2.) Baseline pulmonary function measures 3.) Baseline depression and apathy scales, 4.) Inspiratory resistive load presentation 5.) Reflex cough assessment 6.) fluoroscopic swallow study 7.) Measures of event-related sensory evoked potential (SEP) to an airway stimulus.

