## **Statistical Analysis**

**Aim 1:** A multiple regression analysis will be conducted with the slope magnitude estimation as the outcome and disease duration, age, and sex as the independent variables in addition to their mutual interaction terms. Model selection technique will be adopted to select the optimal parsimonial model deemed for the data. We will also perform subgroup analysis to

compare the slope magnitude estimation between PD patients with PAS (penetration-aspiration scale) no more than 2 and PD patients with PAS greater than 2 by adjusting confounding factors of age, gender and BMI, etc. to demonstrate that reduced slope of magnitude estimation is present in PD patients regardless of PAS status. We will include other swallow and cough outcome variables in this model to determine relationships between dependent variables.

**Aims 2 and 3:** We will first fit a multiple regression model with P1 and N2 peak amplitude and gating ratios as the dependent variable and condition (1 = attend and 2 = ignore) as independent variables by controlling confounding variables including age, gender, BMI, etc. In order to determine the relationship between P1 and N2 peaks and swallow and cough function, we will fit a second multiple regression model with P1 and N2 (amplitude and gating ratio), cough and swallow outcomes as the dependent variables and disease duration as the primary independent variable by controlling confounding variables including age, gender, BMI, etc. Also, model selection technique will be adopted to select the optimal model. Besides the primary outcomes of P1 and N2 peaks, other secondary outcomes such as N1 and P2 amplitudes and gating ratios will be analyzed.

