### **Protocol 2 (aim 4)**

**Participants:** This study will include men and women with PD, and we will recruit from those participating in protocol 1, in addition to the general PD population at UF Fixel Institute for Neurological diseases given protocol 2's larger required N. For participants who did complete protocol 1, the procedures will not be replicated in protocol 2 (therefore these participants would only complete the 2nd and 3rd protocol 2 visits). The inclusionary and exclusionary criteria will be identical to those of protocol 1, with the exception that this protocol will also include people with possible or probable progressive supranuclear palsy (PSP) or multiple systems atrophy (MSA).

**Power Analysis:** To test the hypothesis that the relationship between swallow and cough motor deficits, and reflex cough sensitivity varies as a function of disease duration in PD, we would compare the penetration/aspiration scale change from baseline with 10 to 18 months apart for PD patients. As shown in our pilot study data, the mean (SD) penetration-aspiration scale change from baseline for the first two 10 to 14 months period are 2.08 (1.97) and 2.82 (2.33), respectively. Based on it, to reach a 0.85 power by controlling the type I error rate to 0.05 for detecting this effect size with two-sided test, we would need 155 PD patients.

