**Statistical analysis:** In the statistical analysis, we would fit a linear mixed effects model to take into account the repeated measurement by regarding each subject as a cluster. Specifically, in the analysis, the repeatedly measured outcome, i.e. change of penetration-aspiration scale scores (PAS), C2, cough and swallowing physiology variables from baseline, will be fitted by adjusting for fixed effects terms including baseline PAS, age, sex, medications, levodopa equivalent dose, surgical status, and disease duration (2=third 10-18 month; 1=second 10-18 month; and 0=first 10-18 month) and the random effects term due to participants. Restricted resampling model selection (Zou et al. 2015) technique will be adopted to conduct the valid statistical inference for repeated measurement data and it is also robust to missing data which is particularly useful for this study. **Expected outcomes:** Results of this aim are expected to provide a clinical deliverable in the form of sensitive and specific predictor(s) of airway protection dysfunction that are more customized for patients with different PD durations. As well, because of the study's prospective longitudinal design, this study will also be the first to examine the natural history of cough function in people with PD over the proposed 3-year time period.

**Data storage:** All participant records will be maintained in HIPPA compliant storage. Paper copies of the ICF will be kept in a locked cabinet, in the locked research laboratory of the PI (D2-063 or DG-143; [name]). Paper data collection forms will be kept in a separate, locked file cabinet, also in the research laboratory of the PI. Paper forms will not include participant names or dates; rather participants will be assigned a unique participant ID number that will be kept separate from the name. Electronic database files containing summary data for individual participants and compiled data for all participants will be saved according to participant number within a limited access, password protected folder on the PI's P-drive.

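### The Aim 4 model uses follow-up interval as disease duration and specifies no test of whether cough sensitivity identifies swallowing dysfunction differently within 9 years and at 10+ years of diagnosis

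*Combined protocol and SAP*

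**What the plan says.** **The hypothesis (section 5, Specific Aims).** Hypothesis 4 has two parts. The first is that swallowing safety and physiology will differ over 3 time points. The second is a contrast by years since diagnosis: within 9 years, reduced cough sensitivity will not be a sensitive or specific indicator of swallowing dysfunction, but "for those with a greater disease duration (10+ years), reflex cough sensitivity will be a sensitive and specific biomarker of swallowing dysfunction". The Power Analysis under Protocol 2 restates the second part as the hypothesis that "the relationship between swallow and cough motor deficits, and reflex cough sensitivity varies as a function of disease duration in PD".

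**The analysis (Protocol 2, Statistical analysis).** One linear mixed model is described. Its outcomes are changes from baseline in PAS, C2, and the cough and swallowing physiology variables. The named fixed effects are baseline PAS, age, sex, medications, levodopa equivalent dose, "surgical status, and disease duration (2=third 10-18 month; 1=second 10-18 month; and 0=first 10-18 month". A participant random effect and a model selection technique complete the description. The Expected outcomes text that follows promises sensitive and specific predictors tailored to PD duration, without a method.

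**The schedule.** Swallowing and cough are measured at 3 time points, 10 to 18 months apart. Aim 4 describes this as "cough sensitivity over a 3-year time period in people with PD".

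**The concern.** The term called disease duration in the Aim 4 model is not the disease duration of the hypothesis. Elsewhere the term means years since diagnosis. The Preliminary Studies describe a cohort by it ("participants include 76 men and women with PD, ranging from 1 to 23 years post-diagnosis") and group patients as 1-4, 5-9 and 10+ years post-diagnosis. The analysis for Aims 2 and 3 takes "disease duration as the primary independent variable by controlling confounding variables including age, gender, BMI, etc", and it belongs to Protocol 1, of which the plan says "This prospective experimental study will be completed in one or two study visit(s"; that protocol has no follow-up interval to code.

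The customised predictors are the stated clinical deliverable of Aim 4. If the model is run as written, the study will report change over follow-up. It will not report how well cough sensitivity identifies swallowing dysfunction in either duration group, or whether the groups differ. The definition of dysfunction, the cut-off for C2 or urge-to-cough, and the boundary between duration groups would then be chosen after the data are seen. Sensitivity and specificity depend directly on those choices.

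**Working it through.** **1. What the stated sample size tests.** The pilot mean (SD) PAS "change from baseline for the first two 10 to 14 months period are 2.08 (1.97) and 2.82 (2.33), respectively".
- Difference: 2.82 − 2.08 = 0.74.
- SD of the paired difference, assuming zero within-patient correlation (the plan gives none): √(1.97² + 2.33²) = 3.051.
- Normal approximation for 0.85 power, two-sided 0.05: (3.051 × (1.960 + 1.036) / 0.74)² = 152.6, so 153. The paired t-test gives 155, the plan's figure.

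The 155 therefore reproduces as a comparison of PAS change between two follow-up periods. Years since diagnosis, cough sensitivity and diagnostic accuracy do not enter it.

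**2. Hypothesis against model.**

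| Needed for the second part of Hypothesis 4 | In the Aim 4 analysis |
|---|---|
| Years since diagnosis, within 9 vs 10+ | Not named; disease duration is the study interval |
| Cough sensitivity as predictor | C2 is an outcome only; urge-to-cough slope is listed as a measure but not named in the model |
| Interaction of the two | Not named |
| Definition of swallowing dysfunction | None for Aim 4; a PAS >2 split appears for Aim 1 |
| Cut-off or ROC analysis | None |
| Sensitivity and specificity by duration group | Only an expected outcome |

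**3. Codes against visits.**
- Changes from baseline: 3 visits − 1 baseline = 2, against 3 codes.
- Span of 3 visits: 2 × 10 = 20 to 2 × 18 = 36 months, which agrees with the 3-year period in Aim 4.
- A third interval would need a fourth visit: 3 × 10 = 30 to 3 × 18 = 54 months.
- If the codes are intervals, code 2 has no data. If they are visits, code 0 is baseline, where the change is zero for everyone.

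**4. Illustration of precision for the missing analysis.** The documents give no share of patients at 10+ years, no prevalence of dysfunction and no target accuracy. *Assumed:* 20-40% of the 155 at 10+ years; 30-50% with PAS >2; true sensitivity and specificity 0.80 at 10+ years; one visit per patient. Intervals are Wilson for one proportion and Newcombe for a difference.

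| Quantity | Smallest case | Largest case |
|---|---|---|
| Patients at 10+ years | 0.20 × 155 = 31 | 0.40 × 155 = 62 |
| Cases at 10+ years | 0.30 × 31 ≈ 9 | 0.50 × 62 = 31 |
| 95% CI, sensitivity 0.80 | 0.47-0.95 | 0.63-0.90 |
| Non-cases at 10+ years | 31 − 16 = 15 | 62 − 19 = 43 |
| 95% CI, specificity 0.80 | 0.55-0.93 | 0.66-0.89 |
| Cases within 9 years | 0.30 × 124 ≈ 37 | 0.50 × 93 ≈ 46 |
| 95% CI, difference 0.80 − 0.50 = 0.30 | −0.06 to 0.51 | 0.08 to 0.47 |
| 95% CI, difference 0.80 − 0.60 = 0.20 | −0.16 to 0.42 | −0.01 to 0.38 |

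**The case against.** **The list of fixed effects is open, and model selection could bring in further terms.** The list is open, but no candidate term for cough sensitivity or years since diagnosis is named. Even with such terms added, a linear model of PAS change does not give sensitivity or specificity.

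**Within Protocol 2, follow-up time is used consistently as duration.** The power analysis and the model both do so, which suggests a deliberate choice. That stands as an explanation, but it does not close the gap: two or three years on study cannot stand in for a contrast between patients within 9 years and at 10+ years of diagnosis.

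**The coding mismatch is minor.** Largely fair. An empty third level changes no estimate; only the visit reading, with a baseline row fixed at zero, affects the fit. The first part of Hypothesis 4 is testable once the codes are corrected. The pilot's reference to the first two periods also does not settle how many periods were planned, so the mismatch rests on the three time points alone.

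**The precision figures describe an analysis the plan does not contain.** True, and every input is assumed. With 60% above PAS 2 and 40% at 10+ years (37 vs 56 cases), the 0.20 difference has a 95% CI of 0.006 to 0.36, which just excludes zero. Using repeated visits would also change the intervals. The finding does not depend on these figures.

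**Conclusion.** The concern holds and must be fixed before analysis. The Aim 4 analysis specifies no test of the second part of Hypothesis 4. It names neither years since diagnosis nor cough sensitivity as a predictor, and it describes no estimate of diagnostic accuracy. Its duration term spans at most 36 months within a patient, whereas the team's own separate cohort spans 1 to 23 years post-diagnosis. Separately, three codes are given for two changes from baseline.

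These conclusions come from the text and assume nothing. The sample size of 155 is not disputed. Under the labelled assumptions, a sensitivity of 0.80 at 10+ years would have a 95% CI between 0.47-0.95 and 0.63-0.90, so the analysis is feasible but imprecise and its precision needs planning.

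**What to change.** 1. Rename the coded term time (visit, or months since baseline). Use two levels for the two post-baseline changes, or model the raw scores at all three visits.
2. Add years since diagnosis at baseline as a separate term. For swallowing outcomes, add cough sensitivity (C2 or urge-to-cough slope) and its interaction with years since diagnosis.
3. Define swallowing dysfunction for Aim 4, for example with the PAS >2 split already used in Aim 1, and pre-specify the C2 or urge-to-cough cut-off or an ROC analysis. Report sensitivity and specificity with 95% CIs in each duration group, and their differences, allowing for repeated visits. Because the claim within 9 years is a negative one, also state the performance threshold that would count as not sensitive or not specific.
4. Fix the duration group at baseline and state where 9 to 10 years falls. Follow-up of 20 to 36 months carries patients who start at about 7 to 9 years across the 10-year line.
5. Confirm that years since diagnosis is recorded for every Protocol 2 participant. The disease-status lists do not name it, but the health history questionnaire (Appendix 1) is not visible here, so this is a check and not a demonstrated gap.

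**Cost.** SAP text and one analysis, with no new visit or procedure. The drawback is wide intervals at 10+ years. Balancing recruitment by duration (78 and 77 patients) is optional and would be a design change. With 30-50% above PAS 2, it would give 23 to 39 cases at 10+ years and a 95% CI for a sensitivity of 0.80 of 0.60-0.91 to 0.65-0.90.

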### **Procedures unique to protocol 2:**

Longitudinal measurement of swallowing and cough function: Measures of swallowing and cough will be collected at 3 time points spaced 10 – 18 months apart.

For participants who were also in study protocol 1, those swallowing and cough data will be used for the first time-point in order to reduce participant burden.

Longitudinal measures of Participant disease status: Disease severity (unified Parkinson's disease rating scale and Hoehn & Yahr score), medications, levodopa equivalent dose, and surgical status (specifically deep brain surgery) will be recorded at each study visit.

Pharmacologic and/or surgical therapies for PD may have known and unknown influences on swallowing and/or cough function (i.e., (43)) and will therefore be recorded for this study.

Swallow and cough outcome measures (described in detail in protocol 1):

1. Slope of UtC sensitivity
2. Cough sensitivity: Capsaicin concentration that elicits the 2-cough response (C2)
3. Cough motor (airflow) measures: CPD, PEFR, PEFRT, CVA
4. Swallowing performance measures: Penetration-aspiration scale scores (PAS)
5. Swallowing physiology measures: SRT, dtLVC\_H1, dtLVC\_B1, dLVC, PTT

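### Aim 4: Hypothesis 4 covers differences over three visits, but the only time contrast the plan sets out is, on its best reading, visit 3 against visit 2; no test of the baseline-to-visit-2 change is prespecified

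*Combined protocol and SAP*

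**What the plan says.** Hypothesis 4 (section 5, Specific Aims) states: "Swallowing safety and physiology in people with PD will exhibit significant differences over 3 time points, spaced 10 – 18 months apart". Under Procedures unique to protocol 2, the schedule is: "Measures of swallowing and cough will be collected at 3 time points spaced 10 – 18 months apart". Each participant therefore has one baseline and two follow-up values.

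The Protocol 2 statistical analysis fits a linear mixed model with a participant random effect. Its outcome is "the repeatedly measured outcome, i.e. change of penetration-aspiration scale scores (PAS), C2, cough and swallowing physiology variables from baseline". The fixed effects are baseline PAS, age, sex, medications, levodopa equivalent dose, surgical status and a time term coded "disease duration (2=third 10-18 month; 1=second 10-18 month; and 0=first 10-18 month". The text does not say which coefficient or contrast tests Hypothesis 4.

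The Protocol 2 power analysis says that "we would compare the penetration/aspiration scale change from baseline with 10 to 18 months apart for PD patients". It gives the pilot mean (SD) "change from baseline for the first two 10 to 14 months period are 2.08 (1.97) and 2.82 (2.33), respectively", and arrives at 155 PD patients at 0.85 power, two-sided 0.05.

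**The concern.** The null that matches Hypothesis 4 is that visits 1, 2 and 3 have the same mean. Once the outcome is change from baseline and the first-period change is the reference level, the time term no longer involves baseline. Any worsening between baseline and visit 2 goes into the intercept. The plan does not say that the intercept will be tested. With baseline PAS, age and levodopa dose entered uncentred, the raw intercept is not a mean change in any case.

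At stake is how the main longitudinal hypothesis will be judged. If the period term is read as the test, early worsening that levels off would be reported as no significant difference over time. If it is not, the analyst must choose another test after seeing the data.

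**Working it through.** **Inputs.** From the power analysis: mean changes 2.08 and 2.82, SDs 1.97 and 2.33, n = 155, power 0.85, two-sided 0.05. The within-patient correlation r between the two changes is not given, so values from 0 to 0.7 are assumed. Complete data are assumed throughout.

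**1. What the period term estimates.** Write Y1, Y2, Y3 for the values at the three visits. The first-period change is Y2 - Y1 and the second is Y3 - Y1. With the first as reference, the second-period coefficient is (Y3 - Y1) - (Y2 - Y1) = Y3 - Y2. With two changes per participant only two codes hold data, so treating the code as numeric or categorical gives the same contrast. Covariates that vary by visit make it an adjusted contrast, but do not bring baseline back.

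**2. Reproducing the 155.** The difference is 2.82 - 2.08 = 0.74. The pooled SD is sqrt((1.97² + 2.33²)/2) = sqrt(9.3098/2) = 2.158. Then n = 2 × 2.158² × (1.960 + 1.036)² / 0.74² = 153 (154 using the t distribution), and power at 155 is 0.855. A paired comparison with r = 0 also gives 153; r = 0.3, 0.5 and 0.7 would give 108, 78 and 48. By contrast, testing the pilot visit-2 change against zero needs (1.97 × 2.996 / 2.08)² = 8.05, so about 9 patients. The 155 therefore fits the second- against first-period contrast, not departure from baseline.

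**3. Rejection rates at n = 155.** Changes were simulated as bivariate normal with the pilot SDs (4,000 runs per scenario). The period term was tested as the within-patient difference of the two changes. The three-visit null was tested jointly on 2 degrees of freedom (Hotelling's T²).

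| Mean change at visits 2, 3 | Period term | Joint three-visit test |
|---|---|---|
| 2.08, 2.08 | about 5% | about 100% |
| 0.5, 0.5 | about 5% | 82-97% |
| 1.0, 1.2 | 13-32% | 100% |
| 2.08, 2.82 (pilot) | 84-100% | 100% |

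Ranges cover r from 0 to 0.7. The 5% in the plateau rows does not depend on r, because the expected coefficient is zero. Mixed-model fits (200 runs, baseline PAS as covariate) agreed: for changes 2.08/2.08 and 0.5/0.5 the period term rejected in 4.5% and 5% of runs, the three-visit test in 100% and 92.5%. With no change at all, both rejected in 4.5%.

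**4. Detectable differences at 0.85 power, n = 155.**
- Visit-2 change: 2.996 × 1.97 / sqrt(155) = 0.47 points.
- Visit 3 minus visit 2: 2.996 × SD / sqrt(155), where SD = sqrt(1.97² + 2.33² - 2r × 1.97 × 2.33). This gives 0.73, 0.52 and 0.41 points at r = 0, 0.5 and 0.7 (SD 3.05, 2.17 and 1.70).

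**5. The codes.** Three visits give two changes from baseline, but the model lists three period codes. The third has no data unless there is a fourth visit or the codes mean something else.

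**The case against.** A reader might infer that the planned analysis cannot detect worsening by visit 2. The documents do not support that. The fitted model contains the information: in one simulated plateau data set the intercept with centred baseline PAS was 2.01 (SE 0.16), while the period term was -0.09 (p = 0.56). The plan also never declares the period term to be the test of Hypothesis 4; it sits in a list of adjustment terms. What is missing is a prespecified test, not data or power.

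A reader might also infer that the problem holds whatever the third code means. It does not. If the codes index the three visits, with a baseline row at change zero, the term contrasts with baseline. A simulation of that layout (100 runs, r = 0.5, no covariates) rejected in 100% of runs for changes 2.08/2.08 and 87% for 0.5/0.5. Against this reading, the codes are labelled as 10-18 month periods, the power analysis reports period figures as changes from baseline, and a baseline row would have no variance. The text does not settle it.

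The plateau is not the pattern the sponsor expects. The background calls PD progressive, the pilot change rises from 2.08 to 2.82, and on those means the period term would usually reject. That stands: the harm depends on worsening that is early and then flat or slow. Nor is visit 3 minus visit 2 always the harder contrast to detect; at r = 0.7 its detectable difference (0.41) is below that for visit 2 (0.47).

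Finally, the three-time-point clause of Hypothesis 4 names swallowing safety and physiology only. C2 and the cough airflow measures share the model, but that clause sets no null for them.

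**Conclusion.** The point holds as a mismatch between hypothesis and analysis. On the reading best supported by the text, the only time contrast set out, and the one that the 155 patients power, is visit 3 against visit 2. Hypothesis 4 covers all three visits, and no test of the baseline-to-visit-2 change is named.

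The algebra needs no assumption beyond that reading of the codes. The rejection rates also assume complete data, normally distributed changes with the pilot SDs, and r between 0 and 0.7. The practical loss is large if worsening levels off after visit 2 and small if the pilot pattern recurs. The claim is limited to PAS and the swallow timing measures. This should be fixed before analysis; it does not compromise data collection or the sample size.

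**What to change.** In the Protocol 2 statistical analysis, for PAS and the swallow timing measures, do one of the following:

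- Model the values at all three visits, with visit (baseline, 2, 3) as a categorical fixed effect and a participant random effect. Test Hypothesis 4 by the joint 2-df visit test, and report visit 2 minus baseline and visit 3 minus baseline with 95% confidence intervals.
- Keep change scores, centre the covariates, and prespecify a joint test that the mean change at each follow-up is zero.

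The same model can serve C2 and the cough measures for consistency. Reconcile the three period codes with the three-visit schedule. In the power analysis, state that 155 patients at 0.85 power refers to the second- against first-period change.

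The cost is wording only: same patients, visits and data.
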